## **7.3 PHASE 3. EFFICACY OF THE FRONT OF PACK LABELLING PROPOSALS**

During the last Phase of the Project the efficacy of the re-designed front of pack labelling proposals will be tested in an on-line shopping simulation.

### **7.3.1 Design of the study**

Three-arm randomized controlled trial without blinding

### **7.3.2 Participants**

Participants will be 18 years old or older, who visit a sales point or retail store on regular basis (at least once a week) to make their food purchases.

### **7.3.3 Recruitment**

Recruitment will be done through the Internet. In order to accomplish the required sample size, a company specialized in internet market segmentation in Mexico will be hired. This company will be responsible for disseminating and promoting the on-line shopping website. The recruitment strategy will be designed by this company based on eligibility criteria and sample size requirements to detect statistical differences between intervention groups (See section 8.3.7)

### **7.3.4 Intervention**

The intervention will consist on an on-line purchase simulation with different labelling systems on food products. Participants will be randomly assigned to one of the three conditions using a randomization program: Control group, (no front-of-pack labeling), Label Proposal 1, and Label Proposal 2. Due to the nature of the intervention there will be no blinding of the intervention.

#### **7.3.4.1 *Virtual environment for an online shopping simulation***

A supplier will be hired to develop a virtual environment for the on-line shopping simulation. The virtual environment will consist of five components or moments presented

in the following order: 1) Informed Consent, 2) Eligibility, 3) Collection of demographic data and shopping habits), 4) Virtual Store, y 5) Purchase feedback.

- 1) **Informed Consent.** Before data collection, participants will be asked to give their consent to be part of the study through an Informed Consent Letter (See Appendix). Participants will not be able to give their consent until they read all the consent form (scroll all the way down).
- 2) **Eligibility.** Participants will be asked to confirm they meet the established eligibility criteria. (See section 8.3.2)
- 3) **Demographic data collection. The same** initial questionnaire used in Phase 1 will be used to collect general demographic information (age, sex, information contact), consumption and purchase habits, as well as a series of questions to determine the individual socioeconomic level (Appendix 1). Additionally, information on habitual expenses per week at the supermarket will be requested.
- 4) **Virtual Shop.** Participants will be randomly assigned to one of the three conditions of the interventions (no labelling, proposal 1 and proposal 2). Participants assigned to proposals 1 and 2 will receive a brief introduction to the corresponding label before entering the virtual shop. Once in the shop, participants will receive virtual money (equivalent to that reported on their usual spending per week). The virtual shop will emulate a real supermarket with the following sections: 1) milk and dairy, 2) beverages, 3) salty snacks, 4) bakery and cereals, 5) ready to eat meals and 6) checkout. There will be no restrictions on the order of access to the sections or the number of visited sections. Within each section, participants will be presented a variety of real products with a gradient in nutritional quality. The products will display the label corresponding to the intervention condition as well as the nutritional quality of the product. These products will be selected by the INSP research team (from the healthiest to the least healthy). Foods will be presented on shelves (emulating a real supermarket environment) and will have similar costs to real life. The price of the products will be derived from the food data base used in the first phase of the project. Participants will have the possibility to explore the frontal side of each product's package. As in previous stages, the frontal side will have all elements, including other quality labels (for example, nutritional or health claims), except for any other FoPNL system (for example GDA's or the Nutritional Distinctive). Participants will be able to buy as much food as they wish, based on their assigned budget. Once the purchases have been made, participants will proceed to the checkout area to make their payment.
- 5) **Feedback purchase.** Each participant will receive feedback on the nutritional quality of their purchases. Using a nutrient profiling system, the mean nutritional quality of the food products purchase will be calculated (see section 8.3.4). Based on this information, the participant will receive shopping tips for the selection of healthy foods based on the nutritional content reported on the back of the package.

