##### **7.1.2.1 Participants and y recruitment**

Initial contact and recruitment of participants will be done at different sale points, such as convenience stores, mini supers (Oxxo, Extra, 7 Seven), and retail stores located in different points of Mexico City. The selection of the sale points will be done by convenience, and will include those located in AGEBS (the Mexican equivalent for census tracts) classified as of intermediate socioeconomic level (3, 4 or 5) according to INEGI (National Institute of Statistic and Geography) [42].

An initial questionnaire will be used to explore eligibility criteria, including general demographic information (age, sex, information contact), consumption and purchase habits, as well as a series of questions to determine the individual socioeconomic level (Appendix 1). This rule is an algorithm developed by the Committee of Socioeconomic Levels and measures the extent in which the most important needs of households are satisfied by considering eight characteristics or possessions of the household and schooling of the person who most contributes to household expenses. The eight variables are: 1) schooling of the person who most contributes to expenses, 2) number of rooms, 3) number of bathrooms, 4) number of lamps/bulbs, 5) number of automobiles, 6) possession of a shower, 7) possession of a stove, and 8) Type of flooring. As a result, this rule produces an index that ranks households into seven levels, from A (highest socioeconomic level) to E (lowest socioeconomic level).

The questionnaire will be applied randomly with a systematic skip (every 5 consumers) at the exit of the sale point, after a brief explanation of the study objectives and informed consent. Participants classified as typical C or lower C and meeting inclusion criteria will be invited to participate in focus groups (see below).

There will be a total of five focus groups with an average of 5 to 10 participants each, which often buy and consume (twice a week), at least two of the categories of prepackaged meals and bottled beverages of interest for the study (mentioned in section 8.1.1.2) and meet the following inclusion criteria:

- **Group 1:** Men and women 13 to 15 years old that visit the sales point by themselves, with a specific budget to purchase products.

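### Phase 3 admits weekly food shoppers at any sales point but names only supermarket spending as the source of the virtual budget, with no minimum, so an eligible participant can be randomised unable to produce the primary outcome

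*Combined protocol and SAP*

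**What the plan says.** Section 7.3.2 sets the Phase 3 entry criterion. Participants are adults "who visit a sales point or retail store on regular basis (at least once a week) to make their food purchases". It requires neither supermarket shopping nor a minimum spend.

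Phase 3 does not define a sales point. Phase 1 (section 7.1.2.1) uses the term broadly, for "different sale points, such as convenience stores, mini supers (Oxxo, Extra, 7 Seven), and retail stores".

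Section 7.3.4.1 lists the steps of the simulation in order. At step 3, participants complete the Phase 1 questionnaire, which covers "consumption and purchase habits, as well as a series of questions to determine the individual socioeconomic level (Appendix 1"). The section then adds one spending item: "Additionally, information on habitual expenses per week at the supermarket will be requested".

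At step 4, participants are randomised and enter the shop, where "participants will receive virtual money (equivalent to that reported on their usual spending per week"). The word supermarket is not repeated there. Products "will have similar costs to real life", and the budget binds: "Participants will be able to buy as much food as they wish, based on their assigned budget".

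Sections 7.3.5 and 7.3.6 make the mean nutritional quality of the products bought the primary outcome, analysed by linear regression. The text gives no minimum budget, no handling of a zero or very small reported amount, and no rule for an empty basket.

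**The concern.** The outlets that make a person eligible and the outlets whose spending sets the budget are described differently. Someone who buys food every week at a convenience store or mini super, and not at a supermarket, meets section 7.3.2 and can truthfully answer zero to the spending item. Under the budget rule that person is randomised with nothing to spend. A mean over products bought does not exist when nothing is bought, so the participant counts as randomised but contributes nothing to the primary analysis.

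At stake are some of the planned precision and some of the match between the people enrolled and the people analysed. The loss would come from the plan's own budget rule and can be avoided.

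**Working it through.** **Step 1. Set the sections side by side.**

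- Eligibility (7.3.2): weekly food shopping at any sales point or retail store.
- Scope of the term (7.1.2.1, Phase 1 usage): includes convenience stores and mini supers.
- Spending item named (7.3.4.1, step 3): weekly expense at the supermarket.
- Budget (7.3.4.1, step 4): equal to the reported usual weekly spending, and a limit on purchases.
- Outcome (7.3.5, 7.3.6): mean over products bought.

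If the budget means supermarket spending, it covers fewer outlets than eligibility does. If it means all usual spending, the item named at step 3 asks for the wrong amount. The sections need aligning on either reading.

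**Step 2. Which budgets remove the outcome?** Let B be the budget and p the price of the cheapest product.

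- B < p (including B = 0): nothing can be bought and the mean is undefined.
- B ≥ p: at least one product can be bought and the mean is defined. It is noisier when it rests on few products.

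The documents give no prices, so p is unknown.

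**Step 3. Could the loss differ between arms?** Spending is reported at step 3 and assignment follows at step 4. The budget is therefore a baseline quantity, and budgets below p should balance across arms in expectation.

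**Step 4. The plan's own sample size.** Section 7.3.7 gives at least 273 per group for a difference of 0.3 points, significance level 0.05 and power 80%. It states no SD, so 273 cannot be reproduced from the stated inputs alone. Assuming a two-sided test and equal groups, solve n = 2·SD²·(1.960 + 0.842)² / 0.3² for SD:

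SD = 0.3 × √(273/2) / 2.802 ≈ 1.25

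Putting SD = 1.25 back in gives n = 273. The implied SD would be about 1.41 if the test were one-sided.

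**Step 5. Illustration of lost outcomes.** Let d be the share of randomised participants without an outcome. The values of d are assumed; the documents give none. Suppose exactly 273 are randomised per arm.

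- Evaluable per arm: n = 273 × (1 − d)
- Power = Φ(0.3 / (1.25 × √(2/n)) − 1.960)
- Number to randomise per arm to keep 273 evaluable: 273 / (1 − d), rounded up

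| d | Evaluable per arm | Power | To randomise per arm |
|---|---|---|---|
| 0% | 273 | 80.1% | 273 |
| 5% | 259 | 78.0% | 288 |
| 10% | 246 | 75.8% | 304 |
| 20% | 218 | 70.8% | 342 |

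The extra noise from small but usable budgets is not counted.

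**The case against.** Several points on the other side have force.

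- **The link to supermarket spending is partly inferred.** The budget sentence speaks of usual weekly spending, and the Phase 1 questionnaire (Appendix 1), which covers purchase habits, is not in the available text. It may hold a broader spending question. A reader might infer that the budget certainly rests on supermarket spending alone. The documents show only that this is the sole spending item named, and that it is introduced as an addition to the questionnaire.
- **The broad meaning of sales point comes from Phase 1.** That passage concerns recruitment to focus groups in Mexico City. Phase 3 recruits online under its own criterion and does not refer back. The broad reading is plausible but not stated. Respondents may also count a mini super as a supermarket.
- **A supermarket budget suits a shop built to resemble a supermarket.** That stands, but it would argue for restricting eligibility, which section 7.3.2 does not do.
- **The power loss need not occur.** Section 7.3.7 gives 273 as a minimum, and recruitment (7.3.3) is designed around the required sample size, so participants without an outcome could be replaced by recruiting more. The illustration holds only if recruitment stops at exactly 273 randomised per arm.
- **The affected group may be small.** It requires people who buy food weekly, spend nothing or almost nothing at a supermarket, and read the item literally.

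These points limit the size of the problem. They do not remove the mismatch in wording or supply a rule for a zero budget.

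**Conclusion.** The concern holds as a minor point that is cheap to correct. As written, a person can satisfy eligibility, report a zero amount, be randomised, and be unable to produce the primary outcome. The expected harm is some lost precision and a somewhat narrower analysed population.

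Three stronger conclusions are tempting but not supported:

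- That any small budget invalidates the outcome. One purchased product is enough to define the mean; only a budget below the cheapest product leaves it undefined.
- That the comparison between arms is biased. Spending is reported before assignment.
- That the trial would answer for supermarket shoppers only. Anyone whose reported amount buys at least one product contributes, including people who shop mainly at convenience stores. The limitations section already says that the sample is not representative.

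The real size is unknown. The figures of about 78%, 76% and 71% power rest on assumed losses of 5%, 10% and 20%, a back-solved SD, a two-sided test and a fixed 273 randomised per arm. They show scale and are not a forecast.

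**What to change.** 1. In section 7.3.4.1, step 3, ask for usual weekly spending on food and beverages across all the outlets that count for eligibility under section 7.3.2, and list those outlet types in the question.
2. In step 4, state that this same figure is the virtual budget.
3. Between the two steps, ask participants to re-check any amount that is zero or below the price of the cheapest product in the shop. Do not randomise them if it stays so. Because the check comes before assignment, it leaves the randomised comparison intact.

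Restricting eligibility to supermarket shoppers would also align the sections, but it narrows the population.

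The cost is one reworded question and one entry check on a website that is still to be built. The drawback is that recall across several outlet types is slightly less precise than recall for one. The check does not cover a participant who has money and chooses to buy nothing; that case needs its own rule in the analysis section.

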Strong evidence shows that the use of an acceptable and understood FoPNL by consumers is associated with higher nutritional quality food selection [21]. In this regard, summary FoPNL are perceived as easier to understand in terms of perceived cognitive load, but since attractiveness and liking of the labels seem to be subjective perceptions, these latter aspects differ between individuals and populations [22]. On the other hand, scientific information on the understanding of different FoPNL formats has not been consistent [22]. Thus, most of the studies from European countries suggest that the Multiple Traffic light is the most effective format to increase healthy food selection [5, 6]. However, international research indicates mixed results related to an ideal FoPNL to guide consumers to choose healthy products[7].

In addition, it is not clear how to achieve FoPNL use among consumers with different characteristics [23]. Different factors have been related to the habitual use of FoPNL, such as previous diagnosis of a chronic disease (for example Diabetes), interest in health, attitudes towards a healthy diet, beliefs around the relevance of nutrition labels in guiding food selection, self-efficacy, education degree and nutrition knowledge [23], emphasizing that motivation is considered a key factor for the use of FoPNL. Thus, FoPNL should be

implemented along with dissemination campaigns or education programs to promote the use of FoPNL in population [23].

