### **5.2 SPECIFIC OBJECTIVES**

1. To design alternatives of Front of Pack Labels that are easy to understand and useful in guiding healthy food choices among Mexican consumers.
  - a. To explore how several nutrient profiling systems classify a sample of food products currently available in the Mexican market.
  - b. To explore the acceptability and understanding of Front of Pack Labelling Systems used in the international food market in a sample of Mexican consumers living in urban areas.
  - c. To identify the graphic and language elements of the labelling systems that facilitate the understanding of the message of the labels towards healthy food selection.
  - d. To design Front of Pack labeling proposals considering the graphic and language elements identified in the previous step.
2. To identify which of the proposed labels has the best performance, in terms of acceptability and objective understanding, in a sample of Mexican consumers.

- a. To explore the acceptability and understanding of Front of Pack Labelling Systems used in the international food market in a sample of Mexican consumers living in urban areas.
3. To evaluate the efficacy of the two best labelling proposals to promote healthy food choices using an on-line shopping simulation in a sample of Mexican consumers.

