### 7.3.6 Analysis of the Data

The impact of the two label proposals will be evaluated using a linear regression model, where the outcome will be the mean nutritional quality of the products bought, whereas the independent variable will be the intervention group. The model will be adjusted for the main demographic confounders such as age, sex, civil status, having children and educational attainment and chronic disease. Differences will be considered statistically significant when  $p < 0.05$ . Analysis will be carried out using STATA version 14.0.

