## **9 LIMITATIONS**

---

The sample for the three stages will not be representative of the Mexican population. Therefore, external validity of the results could be limited to people with similar characteristics of the sample. Nevertheless, previous experiences in Mexico show that understanding and acceptability of the different FoPNL alternatives does not differ by socioeconomic levels. We consider that the information collected will provide relevant information for the design and conduction of future studies in the topic of Front of Pack Labelling.

The use of online tools could have a low response rate, limiting the sample size and consequently statistical power to find differences. However, we have considered hiring an expert company in online market segmentation for the dissemination of the online shopping simulation, as well as through websites with a high traffic of users. By reaching a higher number of individuals we will have a better chance of meeting the required sample size.

The current study will not evaluate the effectiveness of the labelling proposal in a real environment. Therefore, results can only be interpreted as purchase intentions. The evaluation of effectiveness of a FoPNL in a real environment has political, logistic and economic implications that go beyond the scope of this Project.

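### Only the label arms are introduced to a label before shopping, so each comparison with control estimates label plus introduction, yet the plan credits the label alone

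*Combined protocol and SAP*

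**What the plan says.** Section 7.3.4 defines the intervention by the labels on the products: "The intervention will consist on an on-line purchase simulation with different labelling systems on food products". The arms are "Control group, (no front-of-pack labeling), Label Proposal 1, and Label Proposal 2". The introduction is not named there.

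It appears in section 7.3.4.1, item 4, after randomisation and before the shop opens: "Participants assigned to proposals 1 and 2 will receive a brief introduction to the corresponding label before entering the virtual shop". The text calls it brief and ties it to the assigned label, but gives no content. Nothing comparable is described for control.

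The result is then credited to the labels:

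- Section 5.2, objective 3: "To evaluate the efficacy of the two best labelling proposals to promote healthy food choices".
- Section 7.3.6: "The impact of the two label proposals will be evaluated using a linear regression model". The only treatment term is the arm ("whereas the independent variable will be the intervention group"), with demographic covariates added.

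Section 9 acknowledges that "The current study will not evaluate the effectiveness of the labelling proposal in a real environment", but does not mention the introduction.

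**The concern.** Participants in a label arm differ from control participants in two ways: they see a label on the packs, and they have just had that label introduced to them. A difference in mean nutritional quality could come from either or both. The introduction could teach people to read the label. It could also simply draw attention to nutrition, in a trial without blinding, just before the outcome is measured.

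The plan gives no ground for treating the introduction as inert. Its own background (section 2.1) says labels should be "implemented along with dissemination campaigns or education programs to promote the use of FoPNL in population".

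Followed as written, the trial would report a combined effect as the effect of the label. Decision makers, whom the plan names as users of the results, could then expect the same effect from a label printed on packs with nothing to introduce it. A lesser point is that the introduction adds a step, and a possible place to leave the study, that control does not have.

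**Working it through.** **1. What the contrasts estimate.** Assume additive effects. Write C for the control mean, L1 and L2 for the label effects, and I1 and I2 for the introduction effects.

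| Contrast | Estimates |
|---|---|
| Proposal 1 − control | L1 + I1 |
| Proposal 2 − control | L2 + I2 |
| Proposal 1 − proposal 2 | (L1 − L2) + (I1 − I2) |

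Every participant with a label has an introduction, and nobody without a label has one. The two indicators are identical across participants, so covariate adjustment cannot separate L from I. In the third row the introductions cancel if I1 = I2. This step needs no assumed number.

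**2. The plan's own figure.** Section 7.3.7 gives 273 per group, a 0.3-point difference, significance level 0.05 and 80% power. Sidedness is not stated; I take it as two-sided. The SD is not readable, because Figure 7 is not shown, so I solve for it:

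SD = 0.3 / [(1.960 + 0.842) × √(2/273)] = 1.251

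An SD of 1.25 returns 273 per arm and 80.1% power. This is a consistency check, not an independent reproduction. A one-sided 0.05 level would imply an SD of about 1.41.

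**3. Significance threshold.** SE = 1.25 × √(2/273) = 0.107. An observed difference of 1.96 × 0.107 = 0.21 points is significant.

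**4. Inert label, introduction raises the mean by b.** The probability of a significant result in favour of the label is Φ(b/SE − 1.96). With b = 0 it is 2.5%.

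| b (points) | share of 0.3 | SD 1.0 | SD 1.25 | SD 1.5 |
|---|---|---|---|---|
| 0.05 | 17% | 8.4% | 6.8% | 5.8% |
| 0.10 | 33% | 21.4% | 15.3% | 11.9% |
| 0.15 | 50% | 41.8% | 28.8% | 21.4% |
| 0.20 | 67% | 64.7% | 46.4% | 34.4% |

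The values of b are assumptions; the documents give none.

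**5. Opposite direction.** If the introduction lowered the mean and the label's true effect were 0.3, power would be Φ((0.3 + b)/0.107 − 1.96): 80.1% at b = 0, 64.7% at b = −0.05 and 46.4% at b = −0.10.

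**6. Proposal 1 versus proposal 2.** With equal introduction effects the net shift is zero and the two-sided error stays at 5%.

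**7. Unequal exit.** Suppose a label arm loses about 5%, 10% or 20% of its participants, leaving 259, 246 or 218 against 273 in control. Power for 0.3 is then about 79%, 78% or 75%. The loss of precision is small. Whether those who leave differ from those who stay cannot be judged from the documents.

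**The case against.** The strongest reply is that the introduction is disclosed. It sits inside the Intervention section, the regression term is the assigned arm with everything in it, and the impact of the label proposals is shorthand for that. On this view no contrast is wrong. Section 2.1 also recommends pairing labels with education, so label plus introduction may be close to the policy of interest. This stands as far as it goes: the package is a legitimate thing to estimate. But the plan never says it is what is being estimated, and the objective and the analysis section name the label alone.

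The documents do not expressly say that control receives nothing. That is an inference, though the natural one: the introduction is assigned to proposals 1 and 2, and control has no label to introduce. If a matched screen is intended, stating so is part of the fix.

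The percentages rest on assumed shifts, a back-solved SD and a two-sided test. Section 2.1 speaks of campaigns and programs, and does not show that a brief screen changes choices. All of this is fair. The figures illustrate what could happen; the finding itself rests on step 1 of the working.

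A neutral control screen would not remove the label-specific teaching. That is also right, and it is why the wording change is needed as well.

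Finally, section 9 already limits the results to purchase intentions. That addresses the artificial setting but not the introduction.

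**Conclusion.** The concern holds. As designed, each label-versus-control comparison estimates label plus introduction, and the plan presents it as the effect of the label. The conclusion follows from the allocation of the introduction and depends on no assumed number, only on the reading that control receives no counterpart.

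The practical size is unknown, as is the direction. Under the assumptions in the working, a modest positive introduction effect would raise the chance of crediting an inert label several-fold above 2.5%, and a negative one would cost substantial power. The comparison between the two labels is largely protected if their introductions are equivalent. The trial remains usable. What needs correcting is what it may conclude, and this should be done before the virtual shop is built, because a control screen cannot be added after data collection.

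**What to change.** 1. In section 7.3.4.1, item 4, give control a pre-shop screen of the same length and format as the label introductions, with neutral content: how to move between sections, view the front of packs and pay. Keep the two label introductions equivalent in length and format. This equalises the extra step, the time and the exit point, but does not remove the label-specific teaching.
2. In sections 7.3.4, 7.3.5, 7.3.6 and 9, define the effect. Suggested wording: *Each label condition consists of the label on packs plus a brief introduction to it. Label-versus-control differences estimate the combined effect and will not be interpreted as the effect of the label alone.*
3. A short description of each introduction in 7.3.4.1 would help readers judge the package; this is secondary.

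The cost is one static screen, a few sentences and a slightly narrower conclusion. The sample size stays at 3 × 273 = 819. Isolating the label's own effect would need at least one further arm (4 × 273 = 1,092), which is not requested.
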